5.2.2. Cycle 1 day -1

To mitigate the risk for TLS, subjects must be receiving tumor lysis prophylaxis, including hydration (oral, intravenous) and treatment with a uric acid reducing agent (allopurinol, rasburicase) per institutional guidelines prior to and during the venetoclax ramp-up period of Cycle 1.

5.2.3. Cycle 1 Venetoclax Ramp Up:

Venetoclax will be administered at a dose of 100 mg (or equivalent) on day 1, 200 mg (or equivalent) on day 2, and 400 mg (or equivalent) on day 3-10 of the first cycle or at the RP2D duration.

During cycle 1 venetoclax dosing ramp up, TLS lab monitoring (K+, uric acid, Phosphorus, Calcium and Creatinine) should occur at pre-dose, 6-8 hours post dose, and 24 hours post dose (inpatient AM labs may substitute for the 24 hour post-dose labs if applicable).

No ramp up is required in subsequent cycles.

5.2.4. Treatment Schedule:

All subjects must complete a screening visit, cycle 1 day 1, cycle 1 day 15 visit, day 1 visits for each new cycle, and an end-of-treatment visit.

Patients may remain on study for up to 12 cycles if the patient demonstrates clinical benefit and no excessive toxicity (i.e. no clinically significant non-hematologic study-drug related grade ≥ 3 toxicity). Patients who are experiencing clinical benefit and have not experienced excessive toxicity may be eligible to continue therapy after discussion with the PI and the discussion documented in the patient's medical record.

Bone marrow biopsy and/or aspiration on day 28 (+/- 7 days); if no morphologic evidence of leukemia, venetoclax should be held and bone marrow should be repeated 2 weeks (+/- 7 days) in the absence of count recovery. Bone marrow biopsy and aspiration after cycle 3 and cycle 5; subsequently bone marrow aspirate and/or biopsy, every 3 cycles or as clinically indicated. No repeat bone marrow is necessary if nonresponse or progressive disease can be unequivocally diagnosed from peripheral blood tests.

Cytogenetics should be performed if abnormal pre-therapy, any time a bone marrow exam is performed. Molecular testing depending on the positive tests pre-study (specific mutations, whole genome sequencing) and should be followed any time a bone marrow exam is performed. Omissions will not be considered as deviations.

Multi-parameter flow cytometry for the presence of leukemia associated immunophenotype (minimal residual disease) any time a bone marrow exam is performed. Omissions will not be considered as deviations.

5.2.5. Outside Physician Participation During Treatment:

Both omacetaxine and venetoclax are self-administered medications. In the event the patient cannot travel to MDACC for a new cycle visit (due to pandemic precautions), a telemedicine visit

including laboratory review is acceptable and medications will be shipped directly to the patient. Local care for the patient includes routine blood work monitoring in between treatment cycles.

1. Communication between the treating physician and/or PI with the outside physician is required prior to the patient returning to the local physician. This will be documented in the patient record.
2. A letter to the local physician outlining the patient's participation in a clinical trial (Dear Doctor Letter) will request local physician agreement to supervise the patient's care.
3. Any protocol required evaluations performed by local physician will be documented by telephone, fax or e-mail.
4. Changes in drug dose and/or schedule must be discussed with and approved by the PI or their representative prior to initiation and will be documented in the patient record.
5. A copy of the informed consent, treatment schema and evaluation during treatment will be provided to the local physician.
6. Documentation to be provided by the local physician will include drug administration records, progress notes, reports of protocol required laboratory and diagnostic studies and documentation of any hospitalizations.
7. The home physician will be requested to report to the physician investigator all life threatening events within 24 hours of documented occurrence.

5.3. Meals and Dietary Requirements:

Venetoclax should be taken together with approximately 240 mL of water and within 30 minutes after the completion of a meal, preferably a low or moderate-fat breakfast.

Subjects should not consume grapefruit or grapefruit products, Seville oranges, or Star fruit within the 3-day period prior to the first venetoclax administration and until the last day of venetoclax is completed due to possible CYP3A mediated metabolic interaction.

A dose missed earlier in a day can be made up later that day as long as it is taken within 6 hours of the missed dose. If more than 6 hours have elapsed, then that dose should be omitted, and the subject should resume treatment with the next scheduled dose.

Any missed doses should be documented in the subject diary and returned for drug accountability.

If vomiting occurs shortly after a dose of VEN, that dose should not be made up later that day. The subject should continue with the dosing schedule on the next day and inform the investigator and document this in the subject diary.

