This study will be a Phase 1b/II single center, open-label, non-randomized clinical trial with the dual primary objectives of assessing the safety and efficacy of omacetaxine in combination with the BCL2 inhibitor venetoclax for patients with RUNX1-mutated relapsed or refractory AML or MDS. Up to 12 cycles will be administered.

Patients will be instructed to self-administer OM at home and return unused intact drug syringes to be disposed of by the study staff. Patients will be given a Research Medication Diary to record the medication taken each day. Patients will be instructed to bring the diary and any unused intact medication syringes with them to all study visits. Any unused drug will be disposed of per institutional standard practice.

4.2 Phase 1b Portion:

A maximum of 12 patients will be treated in Arm A (AML) and Arm B (MDS), respectively. Patients will be enrolled in cohorts of 3 within each arm. The starting dose in both arms will evaluate omacetaxine via subcutaneous injection at a dose of 1.25 mg/m² twice daily for 3 consecutive days on days 2-4, in combination with venetoclax 400mg orally daily on days 1-10 per treatment cycle.

The RP2D will be selected at the end of the Phase 1b portion based on safety data, in Arms A and B independently. Preliminary efficacy and PK data for each dose level may also be considered as appropriate. Once the RP2D has been identified, that Arm will transition to the respective Phase 2 portion.

Table 1 below shows the planned dose levels, with the starting dose being dose level 0. Patients treated in the Phase 1b portion that are removed from study before day 28 for any reason other than toxicity, and have not experienced DLT, will be replaced.

Table 1: Dose de-escalation for omacetaxine and venetoclax

Dose Level	omacetaxine	venetoclax
+1	1.25 mg/m ² BID days 2-4	400mg QDAY days 1-14
0 (starting dose)	1.25 mg/m ² BID days 2-4	400mg QDAY days 1-10
-1	1.25 mg/m ² BID days 2-3	400mg QDAY days 1-10
-2	1.25 mg/m ² BID days 2-3	400mg QDAY days 1-7

Dose levels outside of this table may be considered based on review of patient safety and efficacy and PK data and will be detailed in a subsequent amendment, if applicable.

4.3 Phase 2:

Up to 60 patients will be treated; up to 30 patients with AML (Arm A) and up to 30 patients with MDS (Arm B) at the recommended Phase 2 dose level. Note that based on the Phase 1b portion, the dose level for the Phase 2 portion of Arm A and Arm B may not be the same.

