8.0 STATISTICAL CONSIDERATIONS

This is an open label, Phase 1b/2 trial to determine the safety/tolerability (phase 1b) and preliminary efficacy (phase 2) of omacetaxine in combination with venetoclax for patients with relapsed/refractory acute myeloid leukemia or myelodysplastic syndrome harboring a *RUNX1* mutation.

Phase 1b: A maximum of 24 patients will be enrolled into this part of the study, with up to 12 patients in each arm (AML or MDS). The dose levels are show in Table 1 and the starting dose is dose level 0.

Dose limiting toxicity (DLT) will be graded according to the NCI Common Terminology Criteria for Adverse Events (CTCAE v5) by organ system. DLTs (see 6.2.1 of the protocol) that occurred within the first 1 cycle after treatment will be used for dose escalation/de-escalation decisions. The Bayesian Optimal Interval (BOIN) design (Liu and Yuan, 2015) will be used to determine the MTD of the combination for each arm. The BOIN design identifies the MTD through minimizing the incorrect decisions of dose escalation and de-escalation (i.e., erroneously escalating/deescalating the dose when the current dose is actually higher/lower than the MTD), thereby optimizing the dose assignment for each enrolled patient. The BOIN design is simple to implement and has been shown to have superior performance through simulations. The BOIN design is algorithm-based, which is similar to the traditional “3+3”; however its overall performance is substantially better.

The following design detail applies to each arm separately. The target toxicity rate for the MTD is $\phi = 0.3$. For each arm, we will enroll and treat patients in cohorts of size 3. To guide dose-escalation decisions, if the observed DLT rate at the current dose is ≤ 0.236 , the next cohort of patients will be treated at the next higher dose level; if it is ≥ 0.359 , the next cohort of patients will be treated at the next lower dose level. These boundaries were created when minimizing decision errors such that $\varphi_1 = 0.18$ is the highest toxicity probability that is considered sub-therapeutic (underdosing) and $\varphi_2 = 0.42$ is the lowest toxicity probability that is deemed overly toxic (overdosing). For the purpose of overdose control, doses j and higher levels will be eliminated from further examination if $\Pr(p_j > 0.3 | \text{data}) > 0.95$, where p_j is the true DLT rate of dose level $j, j = -2, -1, 0, 1$. When the lowest dose is eliminated, stop the trial for safety.

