8.4.2. Efficacy Evaluable Population

All patients who complete at least one post-baseline disease status assessment or who discontinue study medication early due to study drug-related toxicity will be considered evaluable for efficacy. Patients who do not meet the aforementioned requirements will be considered non-evaluable for response and may be replaced.

In addition, we will perform a sensitivity analysis for the efficacy endpoint which will include all patients who have received at least one dose of the study treatment (i.e., those who drop off study early due to any reason will be counted as non-responders).

8.4.3. DLT-evaluable population:

Unless doses are missed in Cycle 1 due to DLT(s), a patient must receive at least 70% of the planned doses of venetoclax and omacetaxine to be considered evaluable for DLT. If a patient received fewer doses/days of treatment in the first cycle of treatment for reasons other than a DLT, the patient will be considered non-evaluable for DLT and replaced.

8.5 Analysis Plan:

Descriptive statistics including plots, mean, median and standard deviations will be used to summarize data. For the primary efficacy analysis, we will estimate the ORR for the combination treatment, along with the Bayesian 95% credible interval. The priors for ORR will be (0.2, 0.8) for AML cohort and (0.15, 0.85) for MDS cohort. Event-free survival (EFS) is defined as the time interval between the date of treatment start and the date of [treatment failure, relapse or death from any cause](#). The Kaplan-Meier method will be used to estimate the probabilities of event-free survival (EFS) and overall survival (OS). Log-rank tests will be used to compare among subgroups of patients in terms of EFS or OS. Similar analyses will be performed for the duration of response. MRD negative status and exploratory biomarkers will be summarized graphically and with descriptive statistics. The association between molecular and cellular markers and overall response and/or resistance will be assessed through logistic regression analyses. Paired t-test or Wilcoxon signed rank test will be used to assess the marker change over time. Safety data will be summarized using frequency and percentage, by category and severity.

The Investigator is responsible for completing an efficacy/safety summary report, and submitting it to the IND Office Medical Affairs and Safety Group, for review and approval

- Phase 1b

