After the first 3 evaluable patients, per arm, complete 1 cycle of study treatment, and every 3 evaluable patients thereafter, IND Office approval must be obtained prior to advancing/changing dose levels.

- Phase 2:

After the first 10 evaluable patients, per arm, complete 3 cycles of study treatment, and every 10 patients thereafter.

A copy of the cohort summary should be placed in the Investigator's Regulatory Binder under "sponsor correspondence".

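### Section 5.2.3 fixes the end of cycle 1 venetoclax at day 10 during phase 1b, which contradicts Table 1 at dose levels +1 (14 days) and -2 (7 days)

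*Combined protocol and SAP*

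**What the plan says.** Section 5.2.3 (Cycle 1 Venetoclax Ramp Up) prescribes 100 mg on day 1 and 200 mg on day 2, then "400 mg (or equivalent) on day 3-10 of the first cycle or at the RP2D duration". It names no other end point and does not mention the dose level assigned to the patient's cohort.

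On when the RP2D exists, section 4.2 states: "The RP2D will be selected at the end of the Phase 1b portion based on safety data".

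On the dose levels, section 8.0 states: "The dose levels are show in Table 1 and the starting dose is dose level 0". Table 1 in section 4.2 gives venetoclax as "400mg QDAY days 1-14" at level +1 and "400mg QDAY days 1-7" at level -2, with days 1-10 at levels 0 and -1. Omacetaxine is given on days 2-4 at levels +1 and 0, and on days 2-3 at levels -1 and -2.

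On what drives dose assignment, section 8.0 says that DLTs "that occurred within the first 1 cycle after treatment will be used for dose escalation/de-escalation decisions".

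**The concern.** A dose-finding design needs its dose levels to differ in the period in which toxicity is counted. Here that period is cycle 1. Within the pair 0/+1, and within the pair -1/-2, the omacetaxine schedule is the same and venetoclax duration is the only contrast. A cycle 1 rule that ends venetoclax on day 10 at every level removes that contrast.

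The direction of the error also matters. At level +1 the cohort would be under-treated relative to its label, so its DLT data would describe level 0. At level -2, a cohort moved down because of toxicity would receive more venetoclax than assigned, and its cycle 1 regimen would be that of level -1.

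**Working it through.** No published figure has to be reproduced. The check sets the two texts side by side and does simple arithmetic.

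**Step 1: which end point applies in phase 1b.** Section 5.2.3 offers day 10 or the RP2D duration. Under section 4.2 no RP2D exists while phase 1b patients receive cycle 1. Day 10 remains.

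**Step 2: compare with Table 1.** Milligrams include the ramp-up and assume no reduction for a CYP3A inhibitor: total = 100 + 200 + 400 × (days − 2).

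| Level | Omacetaxine days | Venetoclax days, Table 1 | Venetoclax days, literal 5.2.3 | mg, Table 1 | mg, literal 5.2.3 |
|---|---|---|---|---|---|
| +1 | 2-4 | 14 | 10 | 100 + 200 + 400 × 12 = 5,100 | 3,500 |
| 0 | 2-4 | 10 | 10 | 100 + 200 + 400 × 8 = 3,500 | 3,500 |
| -1 | 2-3 | 10 | 10 | 3,500 | 3,500 |
| -2 | 2-3 | 7 | 10 | 100 + 200 + 400 × 5 = 2,300 | 3,500 |

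**Step 3: size of the discrepancy.**
- Level +1: 14 − 10 = 4 days too few; 4/14 = 28.6%. In mg, 3,500/5,100 = 68.6% of the assigned amount.
- Level -2: 10 − 7 = 3 days too many; 3/7 = 42.9%. In mg, 3,500/2,300 = 152% of the assigned amount.
- Levels 0 and -1: no discrepancy.

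**Step 4: number of distinct cycle 1 regimens.** Omacetaxine per cycle is 1.25 × 2 × 3 = 7.5 mg/m² at +1 and 0, and 1.25 × 2 × 2 = 5.0 mg/m² at -1 and -2. Written as omacetaxine days / last venetoclax day, Table 1 gives 2-4/14, 2-4/10, 2-3/10 and 2-3/7, which is four regimens. Literal 5.2.3 gives 2-4/10 twice and 2-3/10 twice, which is two.

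**Step 5: would the evaluability rule catch it?** Section 8.4.3 requires that "a patient must receive at least 70% of the planned doses of venetoclax and omacetaxine to be considered evaluable for DLT". This is a minimum only. At level -2 the patient receives 10/7 = 143% of the planned venetoclax days, which a minimum cannot flag. At level +1 the patient receives 10/14 = 71.4%, which still passes when doses are counted.

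**Step 6: how often the affected levels are used.** In the plan's own BOIN simulations (section 8.0, Operation Characteristics), the share of patients treated at level -2 plus level +1 is:
- Scenario 1: 24.4 + 1.9 = 26.3%
- Scenario 2: 5.8 + 8.4 = 14.2%
- Scenario 3: 0.4 + 25.9 = 26.3%
- Scenario 4: 0 + 53.2 = 53.2%

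These shares show how often the conflicting instruction would apply. They do not show how often staff would follow it.

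**The case against.** The strongest reply is that the text has only one sensible reading. Section 5.2.3 is a ramp-up rule, placed among the tumor lysis precautions, and its day 10 matches the starting regimen in section 4.2. Its reference to the RP2D shows that duration was expected to vary with the dose level, and RP2D may be loose wording for the level in force. Sections 4.2 and 8.0 point to Table 1 for the dose levels. A reading under which a move from 0 to +1, or from -1 to -2, changes nothing in cycle 1 is absurd enough to correct itself. Lowering the dose on days 1-2 for tumor lysis safety does not imply authority over the number of days.

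There are also practical checks. The trial is single-center, patients keep a medication diary, and section 8.5 says "IND Office approval must be obtained prior to advancing/changing dose levels". Level -2, where the error would be overdosing, is rarely reached: in the simulations it receives 24.4% of 11.8 patients (about 2.9) in scenario 1, and 5.8% of 11.8 (about 0.7) or fewer in the other three.

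Much of this stands. Table 1 is very probably meant to govern, and an unnoticed cohort-wide error is unlikely. Section 5.2.3 applies to cycle 1 only, and RP2D selection rests on safety and efficacy data that are not confined to that cycle.

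It does not remove the conflict. No text gives Table 1 precedence. The sentence states a last dosing day as well as the ramp-up. The reader must already let 5.2.3 override Table 1 on days 1-2 (100 and 200 mg in place of 400 mg), so a simple rule that Table 1 always wins is not available. The IND Office requirement covers changes of dose level; it does not mention checking the days actually given.

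**Conclusion.** The concern holds. In phase 1b, section 5.2.3 as written contradicts Table 1 at levels +1 and -2. It agrees at levels 0 and -1, and in phase 2, where the RP2D duration applies.

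The consequence is conditional. Only if 5.2.3 is followed literally do the four dose levels become two in cycle 1, with 4 venetoclax days too few at +1 (29%) and 3 too many at -2 (43%, or 1,200 mg more with the ramp-up and no CYP3A-inhibitor adjustment). No probability of a dosing error or of a wrong MTD is claimed, and the documents give no basis for one.

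This is a text inconsistency in a dosing instruction. The BOIN design itself is not in question. It should be corrected because the instruction governs exposure in the DLT window, and because at level -2 the error runs in the unsafe direction.

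**What to change.** Reword the 400 mg clause of section 5.2.3, keeping the allowance for equivalent doses, along these lines: *400 mg (or equivalent) from day 3 to the last venetoclax day of the assigned dose level in Table 1 (day 14, 10, 10 or 7 for levels +1, 0, -1 and -2), or of the RP2D in phase 2.*

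If any phase 1b patient has already been treated at level +1 or -2, confirm the number of venetoclax days given in cycle 1.

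The cost is one phrase. The BOIN boundaries, sample size and operating characteristics stay as they are.

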5.4. CYP3 Inducers and Inhibitors

CYP3A inhibitors are discouraged, but allowed with appropriate VEN dose reduction at all study timepoints as per the U.S. Prescribing Information for venetoclax including an 82.5% dose reduction for posaconazole (i.e. venetoclax 70mg qday instead of 400mg) and 75% dose reduction for other strong CYP3A inhibitors (i.e. venetoclax 100mg qday instead of 400mg in combination with voriconazole).

If a moderate CYP3A inhibitor is prescribed on study, a 50% dose reduction of VEN will be required (i.e. 200 mg instead of 400 mg).

5.5 Supportive Care:

Supportive care measures including blood products, infection prophylaxis and growth factors will be administered according to institutional and Leukemia Department guidelines.

Concomitant intrathecal chemotherapy is permitted for treatment or prophylaxis of extramedullary disease and will be captured in the eCRF.

5.6 Management of Myelosuppression:

Myelosuppression and the related adverse events (thrombocytopenia, anemia, neutropenia, febrile neutropenia) are common in both treated and untreated patients with AML and MDS. In addition, patients treated with VEN and OM may experience myelosuppression.

If a patient achieves a clinical response including CR, CRI, MLFS (AML) or mCR (MDS), and they have not recovered ANC \geq 500/uL within 14 days of VEN drug interruption unless it is thought to be due to the underlying disease, VEN dosing may be further interrupted until ANC recovery to \geq 500/uL. GCSF may be administered if in the best interest of the patient.

5.7 Recommended Dose Reductions:

Patients with a response (i.e. no marrow evidence of leukemia) who have prolonged (>42 days) count recovery, may have treatment with omacetaxine and venetoclax interrupted until neutrophils recover to ANC \geq 500/ μ L and platelets to $>50 \times 10^9/L$. After interruption, dose adjustment for venetoclax can be made as follows:

Table 2. Suggested dose modifications for venetoclax-related AEs

Dose Level	Venetoclax dose mg	Venetoclax duration
0 (starting dose)	400	10 days
-1	400	7 days
-2	400	5 days

- A reduction of 2 dose levels may be considered if the toxicity was deemed severe and life threatening by the treating physician, and if it is in the patient's best interest.
- Additional or alternative dose modifications are acceptable when deemed to be in the patient's best interest, after a discussion by the investigator and the PI and with appropriate documentation.

Table 3. Suggested dose modifications for omacetaxine-related AEs

Dose Level	omacetaxine
0	1.25 mg/m ² BID days 2-4
-1	1.25 mg/m ² BID days 2-3
-2	1.25 mg/m ² QDAY days 2-3

- A reduction of 2 dose levels may be considered if the toxicity was deemed severe and life threatening by the treating physician, and if it is in the patient's best interest.
- Additional or alternative dose modifications are acceptable when deemed to be in the patient's best interest, after a discussion by the investigator and the PI and with appropriate documentation.

A patient who has had a dose reduction may have their dose re-escalated provided the patient has remained free of toxicity requiring dose adjustments as defined above for at least 1 month. Escalation will be made by 1 dose-level increment only, and not more frequent than every month.

Treatment interruptions and dose modifications other than the ones mentioned above can be considered after discussion with the PI and proper documentation of the rationale. Dose adjustment/delay of only one of the agents is permissible if the toxicity is most likely judged to be related to one of the agents by the investigator.

6.0 RESPONSE DEFINITIONS:

6.1.1 Primary Efficacy Analysis: Clinical activity assessed based on revised IWG response criteria for AML (Cheson et al., 2003)

The primary endpoint is the overall response rate (ORR), defined as the proportion of patients who had CR (complete remission), CRh (complete remission with incomplete hematologic recovery), CRI (complete remission with incomplete count recovery), PR (partial response) or MLFS (marrow clearance of blasts) within 3 months of treatment initiation among adult patients with AML.

- CR:** Absolute neutrophil count $> 10^3/\mu\text{L}$, platelets $\geq 10^5/\mu\text{L}$, red cell transfusion independence, absence of extramedullary disease, and bone marrow with $< 5\%$ blasts.
- CRi:** Bone marrow with $< 5\%$ blasts, with peripheral neutrophils of $< 1000/\mu\text{L}$ or platelets $\leq 100,000/\mu\text{L}$.
- CRh:** Bone marrow with $< 5\%$ blasts, with peripheral neutrophils of $\geq 500/\mu\text{L}$ AND platelets $\geq 50,000/\mu\text{L}$
- PR:** All of the hematologic values for a CR, but with a decrease of at least 50% in the percentage of blasts, to 5% to 25%, in the bone marrow aspirate.
- MLFS** Bone marrow with $< 5\%$ blasts, absence of extramedullary disease, no hematologic recovery required

Analyses of overall response rate (ORR) as defined by CR + CRi + PR + MLFS, CR rate, CR/CRi rate, CR/CRh rate will be performed for enrolled subjects, with laboratory response assessment occurring +/- 7 days from bone marrow evaluations. The depth of remission such as with exploratory analyses of MRD negativity by flow cytometry and/or concomitant molecular analysis will also be performed.

6.1.2 Primary Efficacy Analysis: Clinical activity assessed based on revised IWG Response Criteria for MDS (Cheson et al., 2006)

The primary endpoint is the overall response rate (ORR), defined as the proportion of patients who had CR (complete remission), PR (partial response), Hematologic Improvement, or mCR (marrow clearance of blasts) within 3 months of treatment initiation among adult patients with MDS.

CR: Absolute neutrophil count $> 10^3/\mu\text{L}$, platelets $\geq 10^5/\mu\text{L}$, hemoglobin $\geq 11 \text{ g/dL}$, and bone marrow with $< 5\%$ blasts. Peripheral dysplasia will be noted.

PR: All of the hematologic values for a CR, but with a decrease of at least 50% in the percentage of blasts, to 5% to 25%, in the bone marrow aspirate.

mCR Bone marrow with $< 5\%$ blasts and decrease by $\geq 50\%$ over pretreatment, no hematologic recovery required.

HI Improvement in neutrophil count, platelets, or red cells (see below)

SD Failure to achieve at least PR, but no evidence of progression for > 8 weeks

Analyses of overall response rate (ORR) as defined by CR + PR + mCR + HI, CR rate, will be performed for enrolled subjects, with laboratory response assessment occurring $+\text{-} 7$ days from bone marrow evaluations. The depth of remission such as with exploratory analyses of MRD negativity by flow cytometry and/or concomitant molecular analysis will also be performed.

6.1.3. Hematologic Improvement Response Criteria:

*Responses must last at least 8 weeks

Proposed Modified International Working Group Response Criteria for Hematologic improvement*	Response criteria (Responses must last at least 8 weeks)†
Erythroid response (pretreatment, $< 11 \text{ g/dL}$)	Hgb increase by $\geq 1.5 \text{ g/dL}$ Relevant reduction of units of RBC transfusions by an absolute number of at least 4 RBC transfusions/8 wk compared with the pretreatment transfusion number in the previous 8 wk. Only RBC transfusions given for a Hgb of $\leq 9.0 \text{ g/dL}$ pretreatment will count in the RBC transfusion response evaluation†
Platelet response (pretreatment, $< 100 \times 10^9/\text{L}$)	Absolute increase of $\geq 30 \times 10^9/\text{L}$ for patients starting with $> 20 \times 10^9/\text{L}$ platelets Increase from $< 20 \times 10^9/\text{L}$ to $> 20 \times 10^9/\text{L}$ and by at least 100%†
Neutrophil response (pretreatment, $< 1.0 \times 10^9/\text{L}$)	At least 100% increase and an absolute increase $> 0.5 \times 10^9/\text{L}$ †
Progression or relapse after HI‡	At least 1 of the following: At least 50% decrement from maximum response levels in granulocytes or platelets Reduction in Hgb by $> 1.5 \text{ g/dL}$ Transfusion dependence

Source: ([Cheson, et al. 2006](#)) Abbreviations: Hgb indicates hemoglobin; RBC: red blood cell; HI: hematologic improvement. Pretreatment counts averages of at least 2 measurements (not influenced by transfusions) ≥ 1 week apart (modification).

†Modification to IWG response criteria ([Cheson, et al. 2003](#)) ‡In the absence of another explanation, such as acute infection, repeated courses of chemotherapy (modification), gastrointestinal bleeding, hemolysis, and so forth.

6.2 Primary Safety Analysis:

The overall incidence and severity of all adverse events using Common Toxicity Criteria v 5.0

An adverse event is any untoward medical occurrence that may present during treatment with a pharmaceutical product but which does not necessarily have a causal relationship with this treatment.

Adverse drug reaction is a response to a drug which is noxious and unintended and which occurs at doses normally used in man for prophylaxis, diagnosis, or therapy of disease or for the modification of physiologic function.

Assessing causal connections between agents and disease is fundamental to the understanding of adverse drug reactions. In general, a drug may be considered a contributory cause of an adverse event if, had the drug not been administered, 1) the event would not have happened at all, 2) the event would have occurred later than it actually did, or 3) the event would have been less severe.

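### CRi and CRh omit the extramedullary condition that CR and MLFS carry, so AML patients with a cleared marrow and persistent extramedullary leukemia count in the primary ORR; CRi also overlaps MLFS

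*Combined protocol and SAP*

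**What the plan says.** Section 6.1.1 prints its own AML response definitions. All four below require marrow blasts under 5%.

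- CR adds neutrophil and platelet thresholds, then "red cell transfusion independence, absence of extramedullary disease, and bone marrow with" blasts under that limit.
- CRi adds only that neutrophils are below 1000/µL or platelets are at or below 100,000/µL. These are upper limits with no floor.
- CRh adds only neutrophils of at least 500/µL and platelets of at least 50,000/µL.
- MLFS reads, after the marrow limit, "blasts, absence of extramedullary disease, no hematologic recovery required".

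The opening of 6.1.1 makes the primary endpoint CR, CRh, "CRI (complete remission with incomplete count recovery), PR (partial response) or MLFS (marrow clearance of blasts) within 3 months" of starting treatment. The Phase II text of Section 8.0 also lists CRh. The analysis paragraph that closes 6.1.1 builds the ORR from CR, CRi, PR and MLFS, without CRh. It then says that the "CR rate, CR/CRi rate, CR/CRh rate will be performed for enrolled subjects".

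Section 5.5 foresees patients with disease outside the marrow: "Concomitant intrathecal chemotherapy is permitted for treatment or prophylaxis of extramedullary disease". No exclusion criterion in Section 3.2 bars them.

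**The concern.** MLFS, the category that asks for no count recovery, demands that extramedullary disease be gone. Two categories named as complete remissions do not. A patient whose marrow has cleared but whose extramedullary leukemia persists is rejected by CR and by MLFS, then admitted to the primary endpoint through CRi or CRh. That endpoint drives the AML go/no-go rule.

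A second, lesser issue comes from the same lines. With no lower count limit on CRi and no stated order among categories, a patient can be CRi and MLFS at once. The CR/CRi rate, which a reader will take as remission with some recovery, then includes patients with no recovery.

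**Working it through.** **Inputs.** The definitions and ORR lists are from Sections 6.1.1 and 8.0. The AML design is from Section 8.0: λ = 0.5, α = 0.51, N = 30, looks every 6 patients, and Table 4 for the AML arm.

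**1. Reproducing the design that uses this endpoint.** With r responses and t toxicities in n patients, the posteriors are Beta(0.2 + r, 0.8 + n − r) for response and Beta(0.2 + t, 0.8 + n − t) for toxicity. Stop if Pr(p_eff > 0.2) < 0.5(n/30)^0.51 or Pr(p_tox ≤ 0.2) < 0.5(n/30)^(0.51/3). This gives response/toxicity boundaries of 0/2, 1/3, 3/4, 4/6 and 6/7 at n = 6, 12, 18, 24 and 30, exactly as printed. Exact enumeration of the four-outcome multinomial gives:

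| Scenario | Claim acceptable, plan (Table 5) | Exact | Average N, plan | Exact |
|---|---|---|---|---|
| p_eff 0.20, p_tox 0.20 | 10.44% | 10.25% | 12.8 | 12.7 |
| p_eff 0.40, p_tox 0.10 | 73.93% | 74.05% | 24.8 | 24.8 |

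The differences are within the error of 10,000 simulations (standard error about 0.3 points for the first row). The design arithmetic is sound; the issue is what counts as a response.

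**2. Applying the printed definitions, marrow blasts 3%.** CR here assumes red-cell transfusion independence.

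| Neutrophils/µL | Platelets/µL | No extramedullary disease | Extramedullary disease present |
|---|---|---|---|
| 100 | 10,000 | CRi, MLFS | CRi |
| 700 | 70,000 | CRh, CRi, MLFS | CRh, CRi |
| 1500 | 70,000 | CRh, CRi, MLFS | CRh, CRi |
| 1500 | 150,000 | CR, CRh, MLFS | CRh |

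**3. No such extramedullary case escapes.** A patient who is not CRi has neutrophils of at least 1000/µL and platelets above 100,000/µL, and therefore meets CRh. So under the ORR lists that include CRh, every patient with marrow below 5% and persistent extramedullary disease is a responder. Under the closing list of 6.1.1, which omits CRh, only those who meet CRi are. A grid over neutrophils 0–3000/µL and platelets 0–300,000/µL confirmed both statements.

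**4. The CRi/MLFS overlap.** Every MLFS patient with neutrophils below 1000/µL or platelets at or below 100,000/µL meets CRi. Both categories count in the ORR, so the ORR does not move; the CR/CRi rate rises by this share of MLFS patients.

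**5. Size.** One patient in 30 is 1/30 = 3.3 percentage points. The final AML rule needs more than 6 responses (and fewer than 7 toxicities), so 7 passes and 6 fails.

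The following is illustration only. *Assume* that the ORR without these patients is 0.20, that they add f to it, and that efficacy and toxicity are independent. The chance of claiming acceptable is then:

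| f | p_tox 0.20 | p_tox 0.10 |
|---|---|---|
| 0 | 10.2% | 23.5% |
| 0.02 | 13.4% | 30.7% |
| 0.05 | 18.1% | 41.6% |
| 0.10 | 24.9% | 57.2% |

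Nothing in the documents says which f applies; it may be close to zero.

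**The case against.** **The extramedullary condition is implied.** Section 6.1.1 says that it follows the revised IWG criteria, and the names of CRi and CRh suggest CR apart from counts. This makes a drafting omission the likely explanation. It does not settle the matter: the section prints its own definitions, states the condition for two categories and leaves it out of two, and nowhere says that it carries over.

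**The ORR already admits residual leukemia.** PR, with 5% to 25% marrow blasts, counts by design. That stands, so a reader should not infer that the ORR was meant to be free of residual disease. The defect is narrower: the same patient is refused by MLFS because of extramedullary disease and accepted through CRi or CRh.

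**The overlap does not touch the primary endpoint.** Correct. The CR/CRi rate has no decision rule and is not among the secondary objectives in Section 1.2.

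**The overlap is not total.** Also correct. A reader might infer that every MLFS patient becomes CRi, or that CR/CRi reduces to marrow blasts below 5%. A patient with neutrophils above 1000/µL and platelets above 100,000/µL who still depends on red-cell transfusion is not CR and not CRi, but is MLFS.

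**The frequency is unknown and the rule is non-binding.** Both true. Section 5.5 covers prophylaxis as well as treatment, so it shows that extramedullary cases are possible, not that they are common.

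**Conclusion.** The point holds on the printed text. In the AML arm, marrow blasts below 5% with persistent extramedullary leukemia counts as a primary response through CRi, or through CRh under the lists in the opening of 6.1.1 and in Section 8.0. The effect on ORR cannot be sized from the documents beyond 3.3 points per patient at n = 30, on an endpoint where one response separates pass from fail. A reader might infer that the stated error rates are wrong or that the ORR is materially inflated. The documents support neither: the operating characteristics reproduce, and the inflation shown in the working rests wholly on assumed frequencies.

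The CRi/MLFS overlap is real but secondary. It raises the CR/CRi rate by the share of MLFS patients with low neutrophils or platelets. No percentage can be attached, because the documents give no expected MLFS share.

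**What to change.** 1. In 6.1.1, add to CRi and CRh the extramedullary condition already written for CR and MLFS.
2. Use one ORR component list in the opening of 6.1.1, in its closing analysis paragraph and in the Phase II text of Section 8.0, so that CRh is treated the same way in all three.
3. For the CR/CRi rate, state a criterion that separates CRi from MLFS. The sponsor should take the threshold from its cited response criteria.
4. Let a patient who meets both CRi and CRh count in both the CR/CRi and the CR/CRh rates. Forcing a single exclusive category would drop that patient from one of them.

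The cost is wording, plus recording extramedullary status at the time of response. CR and MLFS already depend on that assessment, but the Table of Events in 5.2.1, as extracted, marks measurable-disease documentation only at screening, so the later recording should be made explicit. Sample size and stopping boundaries do not change. The reported ORR and CR/CRi rate may be slightly lower.
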